## 12.5.2 Safety endpoints

For all safety analyses, the safety set will be used. All listings and tables will be presented by treatment group.

Safety summaries (tables, figures) include only data from the on-treatment period with the exception of baseline data which will also be summarized where appropriate (e.g. change from baseline summaries). In addition, a separate summary for death including on treatment and post treatment deaths will be provided. In particular, summary tables for adverse events (AEs) will summarize only on-treatment events, with a start date during the on-treatment period (treatment-emergent AEs).

The on-treatment period lasts from the date of first administration of study treatment to 1 week after the last actual administration of any study treatment.

# Adverse events

All information obtained on adverse events will be displayed by treatment group and subject.

The number (and percentage) of subjects with treatment emergent adverse events (events started after the first dose of study medication or events present prior to start of double-blind treatment but increased in severity based on preferred term) will be summarized in the following ways:

- by treatment, primary system organ class and preferred term.
- by treatment, primary system organ class, preferred term and maximum severity.
- by treatment, Standardized MedDRA Query (SMQ) and preferred term.

Separate summaries will be provided for study medication related adverse events, death, serious adverse events, other significant adverse events leading to discontinuation. A subject with multiple adverse events within a primary system organ class is only counted once towards the total of the primary system organ class.

# Vital signs

All vital signs data will be listed by treatment group, subject and visit/time, and if ranges are available, abnormalities will be flagged. Summary statistics will be provided by treatment and visit/time.

# 12-lead ECG

All ECG data will be listed by treatment group, subject and visit/time, and abnormalities will be flagged. Summary statistics will be provided by treatment and visit/time.

# Clinical laboratory evaluations

All laboratory data will be listed by treatment group, subject, and visit/time, and if normal ranges are available, abnormalities will be flagged. Summary statistics will be provided by treatment and visit/time.

Shift tables using the low/normal/high/ (low and high) classification will be used to compare baseline to the worst on-treatment value.

#### 12.5.3 **Pharmacokinetics**

Descriptive statistics of QBW251 plasma concentration data will be provided by treatment and visit/sampling time point, including the frequency (n, %) of concentrations below the lower limit of quantification (LLOQ). Summary statistics of QBW251 plasma concentration data and PK parameters will include mean (arithmetic and geometric), SD, CV (arithmetic and geometric), median, minimum, and maximum. An exception to this is Tmax, where median, minimum, and maximum will be presented.

Concentrations below LLOQ will be treated as zero in summary statistics and for PK parameter calculations.

## **Patient Reported Outcomes and Exacerbations** 12.5.4

# Subject reported outcomes

Cough and Sputum Assessment Questionnaire (CASA-Q) and St. George's Respiratory Questionnaire (SGRQ) domain scores, COPD assessment test (CAT), EQ-5D-3L and EXACT-PRO questionnaire data will be summarized by treatment and visit. Prespecified sub-groups and correlation analysis are provided in the SAPCOPD exacerbations based on **EXACT PRO Questionnaire.** 

The following analyses will be performed to explore any differences in the exacerbation events that occur in QBW251 vs placebo:

# 1) Time to first exacerbation

The time-to-event analyses will be carried out only upon sufficient number of exacerbation events occur during the study to estimate the median in either of the treatment groups.

The time to the first on-treatment exacerbation (event) is defined as the start date of first exacerbation minus the date of randomization +1. Subjects who do not experience an exacerbation or discontinued earlier without an exacerbation will be censored for analyses purposes.

The hazard ratios for QBW251 compared with placebo and their corresponding 80% confidence intervals will be computed using Kaplan-Meier method. The stratification factor may include number of exacerbations.

The Kaplan-Meier estimates of the survival functions for each treatment will be plotted.

# 2) Annualized rate of COPD exacerbations

The total frequency of COPD exacerbations over the 12 week treatment period will be analyzed using a generalized linear model assuming a negative binomial distribution. The time at risk for a subject is defined as the length of time the subject is on treatment and the log (length of time) will be used as the offset variable in the model. The model will include treatment, antibiotic use, and the number of exacerbations in the past 12 months prior to screening as categorical variables. An estimate of the rate ratio together with 80% confidence intervals and corresponding p-value will be presented.

# 3) The percentage of subjects experiencing at least a COPD exacerbation

The proportion of subjects with at least one COPD exacerbation will be analyzed using logistic regression. The model will include treatment, antibiotic use, and the number of exacerbations in the past 12 months prior to screening as categorical variables. The estimated odds ratios will be displayed along with the associated 80% confidence intervals.

## 12.6 Analysis of exploratory endpoints

Commercially Confidential Information

## 12.7 Interim analyses

Commercially Confidential Information

# 12.8 Sample size calculation

Commercially Confidential Information

# 13 Ethical considerations and administrative procedures

# 13.1 Regulatory and ethical compliance

This clinical study was designed and shall be implemented, executed and reported in accordance with the International Conference on Harmonisation (ICH) Harmonized Tripartite Guidelines for Good Clinical Practice, with applicable local regulations (including European Directive 2001/20/EC, US CFR 21), and with the ethical principles laid down in the Declaration of Helsinki.

# 13.2 Responsibilities of the investigator and IRB/IEC

Before initiating a trial, the investigator/institution must obtain approval/favorable opinion from the Institutional Review Board/Independent Ethics Committee (IRB/IEC) for the trial protocol, written informed consent form, consent form updates, subject recruitment procedures (e.g. advertisements) and any other written information to be provided to subjects. Prior to study start, the investigator is required to sign a protocol signature page confirming his/her agreement to conduct the study in accordance with these documents and all of the instructions and procedures found in this protocol and to give access to all relevant data and records to Novartis

monitors, auditors, Novartis Quality Assurance representatives, designated agents of Novartis, IRBs/IECs, and regulatory authorities as required. If an inspection of the clinical site is requested by a regulatory authority, the investigator must inform Novartis immediately that this request has been made.

## 13.3 Publication of study protocol and results

The protocol will be registered in a publicly accessible database such as clinicaltrials gov and as required in EudraCT. In addition, after study completion and finalization of the study report the results of this trial will be submitted for publication and posted in a publicly accessible database of clinical trial results, such as the Novartis clinical trial results website and all required Health Authority websites (e.g. Clinicaltrials.gov, EudraCT etc.).

For details on the Novartis publication policy including authorship criteria, please refer to the Novartis publication policy training materials that were provided to you at the trial investigator meetings.

## 13.4 **Quality Control and Quality Assurance**

Novartis maintains a robust Quality Management System (QMS) that includes all activities involved in quality assurance and quality control, to ensure compliance with written Standard Operating Procedures as well as applicable global/local GCP regulations and ICH Guidelines.

Audits of investigator sites, vendors, and Novartis systems are performed by auditors, independent from those involved in conducting, monitoring or performing quality control of the clinical trial. The clinical audit process uses a knowledge/risk based approach.

Audits are conducted to assess GCP compliance with global and local regulatory requirements, protocols and internal SOPs, and are performed according to written Novartis processes.

## 14 Protocol adherence

This protocol defines the study objectives, the study procedures and the data to be collected on study participants. Additional assessments required to ensure safety of subjects should be administered as deemed necessary on a case by case basis. Under no circumstances including incidental collection is an investigator allowed to collect additional data or conduct any additional procedures for any purpose involving any investigational drugs under the protocol, other than the purpose of the study. If despite this interdiction prohibition, data, information, observation would be incidentally collected, the investigator shall immediately disclose it to Novartis and not use it for any purpose other than the study, except for the appropriate monitoring on study participants.

Investigators ascertain they will apply due diligence to avoid protocol deviations. If an investigator feels a protocol deviation would improve the conduct of the study this must be considered a protocol amendment, and unless such an amendment is agreed upon by Novartis and approved by the IRB/IEC and Health Authorities, where required, it cannot be implemented.

#### 14.1 **Protocol amendments**

Any change or addition to the protocol can only be made in a written protocol amendment that must be approved by Novartis, health authorities where required, and the IRB/IEC prior to implementation.

Only amendments that are required for subject safety may be implemented immediately provided the health authorities are subsequently notified by protocol amendment and the reviewing IRB/IEC is notified.

Notwithstanding the need for approval of formal protocol amendments, the investigator is expected to take any immediate action required for the safety of any subject included in this study, even if this action represents a deviation from the protocol. In such cases, Novartis should be notified of this action and the IRB/IEC at the study site should be informed according to local regulations.

# 16 Appendices

# 16.1 Appendix 1: Clinically notable laboratory values and vital signs

The central laboratory will flag laboratory values falling outside of the normal ranges on the central laboratory reports. Investigators are responsible for reviewing these abnormal values for clinical significance, signing the laboratory reports to indicate their review, and reporting values considered clinically significant in the appropriate eCRF.

Any clinically significant abnormal laboratory value should be evaluated and followed-up by the investigator until normal or a cause for the abnormality is determined.

See Section 16.2 for specific liver event and laboratory test trigger definitions and follow-up requirements.

For ECGs, a notable QTc value is defined as a QTcF (Fridericia) interval of  $\geq$  450 msec for males or  $\geq$  460 msec for females – all such ECGs will be flagged by the Central ECG reading and require assessment for clinical relevance and continuance of the subject by the Investigator.

# 16.2 Appendix 2: Liver event and Laboratory trigger Definitions and

Table 16-1 Liver event and laboratory trigger definitions

**Follow-up Requirements** 

	, ,,	
Definition/ threshold		
LIVER LABORATORY TRIGGERS	
 
3 x ULN < ALT / AST ≤ 5 x ULN
 
1.5 x ULN < TBL ≤ 2 x ULN
 
	
LIVER EVENTS	
 
ALT or AST > 5 × ULN
 
	
	
 
ALP > 2 × ULN (in the absence of known bone pathology)
 
	
	
 
TBL > 2 × ULN (in the absence of known Gilbert syndrome)
 
	
	
 
ALT or AST > 3 × ULN and INR > 1.5
 
	
	
 
Potential Hy's Law cases (defined as ALT or AST > 3 × ULN and TBL > 2 × ULN [mainly conjugated fraction] without notable increase in ALP to > 2 × ULN)
 
	
	
 
Any clinical event of jaundice (or equivalent term)
 
	
	
 
ALT or AST > 3 × ULN accompanied by (general) malaise, fatigue, abdominal pain, nausea, or vomiting, or rash with eosinophilia
 
	
	
 
Any adverse event potentially indicative of a liver toxicity*
 
	

\*These events cover the following: Hepatic failure, fibrosis and cirrhosis, and other liver damagerelated conditions; the non-infectious hepatitis; the benign, malignant and unspecified liver neoplasms TBL: total bilirubin; ULN: upper limit of normal

Table 16-2 Follow up requirements for liver events and laboratory triggers

Criteria	Actions required	Follow-up monitoring
Potential Hy's Law case a	
 
Discontinue the study treatment immediately
 
	ALT, AST, TBL, Alb, PT/INR, ALP and GGT until resolution c
	
 
Hospitalize, if clinically appropriate
 
	(frequency at investigator discretion)
	
 
Establish causality
 
	
	
 
Record the AE and contributing factors (e.g. conmeds, med hx, lab) in the appropriate CRF
 
	
ALT or AST		
> 8 × ULN	
 
Discontinue the study treatment immediately
 
	ALT, AST, TBL, Alb, PT/INR, ALP and GGT until resolution c
	
 
Hospitalize if clinically appropriate
 
	(frequency at investigator discretion)
	
 
Establish causality
 
	
	
 
Record the AE and contributing factors (e.g. conmeds, med hx, lab) in the appropriate CRF
 
	
> 3 × ULN and INR > 1.5	
 
Discontinue the study treatment immediately
 
	ALT, AST, TBL, Alb, PT/INR, ALP and GGT until resolution c
	
 
Hospitalize, if clinically appropriate
 
	(frequency at investigator discretion)
	
 
Establish causality
 
	
	
 
Record the AE and contributing factors (e.g. conmeds, med hx, lab) in the appropriate CRF
 
	
> 5 to ≤ 8 × ULN	Repeat LFT within 48 hours	ALT, AST, TBL, Alb, PT/INR, ALP and GGT until resolution c
	
 
If elevation persists, continue follow-up monitoring
 
	(frequency at investigator discretion)
	
 
If elevation persists for more than 2 weeks, discontinue the study drug
 
	
	
 
Establish causality
 
	
	
 
Record the AE and contributing factors (e.g. conmeds, med hx, lab) in the appropriate CRF
 
	

Criteria	Actions required	Follow-up monitoring	
> 3 × ULN accompanied by symptoms b	
 
Discontinue the study treatment immediately
 
	ALT, AST, TBL, Alb, PT/INR, ALP and GGT until resolution o (frequency at investigator discretion)	
	
 
Hospitalize if clinically appropriate
 
		
	
 
Establish causality
 
		
	
 
Record the AE and contributing factors (e.g. conmeds, med hx, lab) in the appropriate CRF
 
		
> 3 to ≤ 5 × ULN (subject is asymptomatic)	
 
Repeat LFT within the next week
 
	Investigator discretion  Monitor LFT within 1 to 4	
	
 
If elevation is confirmed, initiate close observation of the subject
 
	weeks	
ALP (isolated)			
> 2 × ULN (in the absence of known bone pathology)	
 
Repeat LFT within 48 hours
 
	Investigator discretion  Monitor LFT within 1 to 4	
	
 
If elevation persists, establish causality
 
	weeks or at next visit	
	
 
Record the AE and contributing factors (e.g. conmeds, med hx, lab) in the appropriate CRF
 
		
TBL (isolated)			
> 2 × ULN (in the absence of known Gilbert syndrome)	
 
Repeat LFT within 48 hours
 
	ALT, AST, TBL, Alb, PT/INR, ALP and GGT until resolution c	
	
 
If elevation persists, discontinue the study drug immediately
 
	(frequency at investigator discretion)  Test for hemolysis (e.g.	
	
 
Hospitalize if clinically appropriate
 
	reticulocytes, haptoglobin, unconjugated [indirect] bilirubin)	
	
 
Establish causality
 
	•	
	
 
Record the AE and contributing factors (e.g. conmeds, med hx, lab) in the appropriate CRF
 
		
> 1.5 to ≤ 2 × ULN (subject is asymptomatic)	Repeat LFT within the next week	Investigator discretion  Monitor LFT within 1 to 4	
	
 
If elevation is confirmed, initiate close observation of the subject
 
	weeks or at next visit	

Criteria	Actions required	Follow-up monitoring	
Jaundice	Discontinue the study treatment immediately	ALT, AST, TBL, Alb, PT/INR, ALP and GGT until resolution c (frequency at investigator discretion)	
	Hospitalize the subject		
	Establish causality	discretion)	
	
 
Record the AE and contributing factors (e.g. conmeds, med hx, lab) in the appropriate CRF
 
		
Any AE potentially indicative of a liver toxicity*	
 
Consider study treatment interruption or discontinuation
 
	Investigator discretion	
	
 
Hospitalization if clinically appropriate
 
		
	
 
Establish causality
 
		
	
 
Record the AE and contributing factors (e.g. conmeds, med hx, lab) in the appropriate CRF
 
		

<sup>aElevated ALT/AST > 3 × ULN and TBL > 2 × ULN but without notable increase in ALP to > 2 × ULN b(General) malaise, fatigue, abdominal pain, nausea, or vomiting, or rash with eosinophilia cResolution is defined as an outcome of one of the following: (1) return to baseline values, (2) stable values at three subsequent monitoring visits at least 2 weeks apart, (3) remain at elevated level after a maximum of 6 months, (4) liver transplantation, and (5) death.

Based on investigator's discretion investigation(s) for contributing factors for the liver event can include: Serology tests, imaging and pathology assessments, hepatologist's consultancy; obtaining more detailed history of symptoms and prior or concurrent diseases, history of concomitant drug use, exclusion of underlying liver disease.

# 16.3 Appendix 3: Specific renal alert criteria, Actions and Event Follow-up

Table 16-3 Specific Renal Alert Criteria and Actions

Renal Event	Actions
Confirmed serum creatinine increase 25 – 49%	
 
Consider causes and possible interventions
 
Follow up within 2-5 days
 

Serum creatinine increase 50 % + OR if <18 years old, eGFR 35 mL/min/1.73 m 	
 
Consider causes and possible interventions
 
Repeat assessment within 24-48h if possible
 
Consider drug interruption or discontinuation unless other causes are diagnosed and corrected
 
Consider subject hospitalization and specialized treatment
 

New onset dipstick proteinuria ≥ 3+ OR Protein-creatinine ratio (PCR) ≥ 1g/g Cr (or mg/mmol equivalent as converted by the measuring laboratory)	
 
Consider causes and possible interventions
 
Assess serum albumin & serum total protein
 
Repeat assessment to confirm
 
Consider drug interruption or discontinuation unless other causes are diagnosed and corrected
 

New onset hematuria ≥ 3+ on urine dipstick	
 
Repeat assessment to confirm
 
Distinguish hemoglobinuria from hematuria
 
Urine sediment microscopy
 
Assess sCr
 
Exclude infection, trauma, bleeding from the distal urinary tract/bladder, menstruation
 
Consider bleeding disorder
 

+ Corresponds to KDIGO criteria for Acute Kidney Injury

Additional specialized assessments are available to assess renal function or renal pathology.

(Note: In exceptional cases, when a nephrologist considers a renal biopsy, it is recommended to make slide specimen available for evaluation by the RSG to potentially identify project-wide patterns of nephrotoxicity.)

Whenever a renal event is identified, a detailed subject history and examination are indicated to identify and potentially eliminate risk factors that may have initiated or contributed to the event:

- Blood pressure assessment (after 5-minute rest, with an appropriate cuff size)
- Signs and symptoms like fever, headache, shortness of breath, back or abdominal pain, dysuria or hematuria, dependent or periorbital edema
- Changes in blood pressure, body weight, fluid intake, voiding pattern, or urine output

Concomitant events or procedures such as trauma, surgical procedures, cardiac or hepatic failure, contrast media or other known nephrotoxin administration, or other diseases or causes, e.g., dehydration due to delirium, tumor lysis

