# 9 Study discontinuation and completion

#### 9.1 **Discontinuation**

## 9.1.1 **Discontinuation of study treatment**

Discontinuation of study treatment for a subject occurs when study treatment is stopped earlier than the protocol planned duration, and can be initiated by either the subject or the investigator.

The investigator must discontinue study treatment for a given subject if, he/she believes that continuation would negatively impact the subject's well-being.

Study treatment must be permanently discontinued for a subject under the following circumstances:

- Subject/guardian decision
- Pregnancy
- Use of prohibited treatment as per recommendations in the prohibited treatment Section 6.2.2
- Any situation in which study participation might result in a safety risk to the subject (e.g. hospitalization)
- Following emergency unblinding

or

- Emergence of AE reported as severe and suspected to be related to investigational drug or an SAE reported and suspected to be related to investigational drug
- Emergence of an SAE not suspected to be related to investigational drug in a subject with a verified exposure above the threshold AUC0-24h≥91,700 ng\*h/ml. The investigator must permanently discontinue the investigational study drug as soon as possible upon receipt of the PK results.
- A subject with a verified exposure above the upper range of the individual animal (monkey) model exposure (AUC0-24h≥159,000 ng\*h/ml). The investigator must stop study drug as soon as possible upon receipt of the PK results.
- Any laboratory abnormalities that in the judgment of the investigator, taking into consideration the subject's overall status, prevents the subject from continuing participation in the study
- Any liver event requiring immediate discontinuation of study treatment, as specified in Table 16-2
- Individual serum creatinine increase  $\geq 50\%$  compared to baseline (must be confirmed). Confirmation of the assessment should be made as quickly as possible after an abnormal result is received. A renal event leading to subject discontinuation should be followed up until event resolution (Serum Cr within 10% of baseline), or event stabilization (Serum Creatinine level within  $\pm 10\%$  variability over last 6 months)
- Study drug can be temporarily interrupted as a response to the occurrence of adverse events that do not fulfill the requirements above described for permanent discontinuation (refer to Section 6.5.1).

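### For a confirmed creatinine rise of at least 50%, section 9.1.1 makes permanent discontinuation mandatory while Table 16-3 leaves it to judgement, and nothing says which text prevails

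*Protocol*

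**What the plan says.** Protocol section 9.1.1 introduces its list with "Study treatment must be permanently discontinued for a subject under the following circumstances". One bullet on that list begins "Individual serum creatinine increase", sets the limit at 50% or more, and continues "compared to baseline (must be confirmed). Confirmation of the assessment should be made as quickly as possible after an abnormal result is received". The rest of the bullet deals with follow-up and does not mention an alternative cause. The last item of the list allows temporary interruption, but for "adverse events that do not fulfill the requirements above described for permanent discontinuation".

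In Appendix 3 (section 16.3), Table 16-3 has a row that begins "Serum creatinine increase 50" (per cent). Its actions are to look for causes, then "Repeat assessment within 24-48h if possible", then "Consider drug interruption or discontinuation unless other causes are diagnosed and corrected", and finally to think about hospital admission and specialist care. The third action also appears in the proteinuria row; the creatinine row is the one at issue here. The row above it, for rises of 25 to 49%, is limited to confirmed results. The 50% row carries no such limit.

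On cross-references, the liver bullet in section 9.1.1 reads "Any liver event requiring immediate discontinuation of study treatment, as specified in Table 16-2". The renal bullet names no table. Section 10.2.2 on renal monitoring refers only to the assessment schedule.

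**The concern.** Two parts of the protocol address the same laboratory finding at the same threshold and give instructions of different strength. An investigator who receives such a result may well turn first to the appendix devoted to renal alerts and actions. Nothing there shows that the body of the protocol makes permanent discontinuation mandatory once the rise is confirmed.

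What is at stake is mainly consistent safety conduct: subjects with the same confirmed result could be managed differently according to which page the site consults. A secondary point is that stopping treatment before 12 weeks is the first intercurrent event of the primary estimand (Protocol 12.4.1, SAP 6.1.1). Uneven handling could therefore alter which subjects have that event.

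**Working it through.** No arithmetic applies, because neither document gives an expected frequency of creatinine rises. The check sets the two texts side by side.

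| Feature | Section 9.1.1 | Table 16-3, 50% row |
|---|---|---|
| Threshold | 50% or more over baseline | 50%; no comparison sign is legible in the text at hand, but the row above ends at 49%, so 50% and over is the natural reading |
| Status of the result | Must be confirmed | Not stated; a repeat is one of the actions, where possible |
| Force | Mandatory | To be considered |
| Action | Permanent stop; interruption is for events that do not meet the list | Interruption or discontinuation |
| Another cause found and corrected | No effect stated | Lifts the prompt to consider stopping |
| Pointer to the other text | None | None |

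Three situations then follow.

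1. **First abnormal result, not yet confirmed.** The section 9.1.1 criterion is not yet met, so temporary interruption is still open under that section. The repeat in Table 16-3 is a route to confirmation. The texts are compatible.
2. **Rise confirmed, no other cause found.** Section 9.1.1 requires a permanent stop. Table 16-3 asks the site to consider interruption or discontinuation. A permanent stop satisfies both texts; interruption alone fits only the table.
3. **Rise confirmed, another cause found and corrected.** Section 9.1.1 still requires a permanent stop. Table 16-3 no longer prompts one. Continuing or resuming treatment fits only the table.

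In situations 2 and 3 the table leaves open a course that section 9.1.1 closes.

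The next question is whether the table is confined to situation 1. Three features of the text speak against that:

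- The table does not say that its 50% row is for unconfirmed results only, and it has no row or instruction for what follows the repeat.
- Finding and correcting another cause may take longer than a repeat within 24 to 48 hours, so the exception can reach the confirmed stage.
- Where the protocol intends a two-step rule it can spell one out. The isolated bilirubin row of Table 16-2 gives a repeat test and then a separate instruction if the elevation persists. The 50% creatinine row has no second step.

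**The case against.** The strongest answer is that the texts are sequential. The 25 to 49% row is restricted to confirmed results and the 50% row is not, which suggests that the latter is a first-alert step. Section 9.1.1 then supplies the step after confirmation, and an alert table need not repeat the mandatory list. The creatinine end points for follow-up also agree between section 9.1.1 and Table 16-4 (within 10% of baseline, or within ±10% over the last 6 months), which suggests that the two parts were meant to work together. This stands for the period before confirmation. It does not settle what happens afterwards, because the table's interruption option and its exception for other causes have no counterpart in section 9.1.1.

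Four stronger readings are tempting, and the documents do not support them.

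- *The two rules are opposites.* The table permits discontinuation, and its exception removes a prompt to consider stopping without instructing the site to continue. A site that follows section 9.1.1 breaches nothing in the table. One text is stricter; the other does not forbid the strict course.
- *Any 50% rise ends treatment under section 9.1.1.* The rise has to be confirmed first.
- *The primary comparison is compromised.* No number of affected subjects is given. Clinically significant renal disease and creatinine abnormalities are exclusions (section 5.2), site staff are blinded, and subjects who stop treatment are asked to return for assessments. No effect on the primary comparison is shown.
- *The protocol calls the drug's safety profile unestablished.* The remark in section 9.2 concerns supplying the drug after the study under lighter monitoring. It is not a general statement about this monitored trial.

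**Conclusion.** The inconsistency is real, and it is confined to confirmed rises of 50% or more. For those subjects section 9.1.1 leaves one course, a permanent stop, while Table 16-3 leaves three: stop, interrupt, or carry on after another cause has been corrected. Neither text refers to the other, and no order of precedence is stated.

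The number of subjects concerned is unknown and may be small in a trial of about 100 randomized subjects treated for 12 weeks. The point deserves correction because it is a safety rule that sites should apply in the same way. The consequence for the estimand is possible but secondary and unquantified.

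This rests on two assumptions: that the 50% row means 50% and over, and that no text withheld from the public version settles the precedence. This review takes no position on which rule is clinically right.

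**What to change.** Reconcile section 9.1.1 and the 50% row of Table 16-3 into one rule. It should state:

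- which action applies to a first result and which to a confirmed one;
- what counts as confirmation, and what follows if a repeat cannot be obtained;
- whether temporary interruption is available at each stage;
- whether a diagnosed and corrected alternative cause changes the action.

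Then add a pointer from the renal bullet in section 9.1.1 and from section 10.2.2 to Table 16-3, and one back from the table, as is already done for the liver bullet and Table 16-2. The clinical content of the rule is the sponsor's decision.

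The cost is a short protocol amendment with the approvals described in section 14.1. The change needs no new data and no change to the analysis. The SAP (section 1.4) records a decision to stop the trial before completion, which limits the benefit for this trial's own subjects but does not remove the inconsistency.
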